9.1. Screening

Subjects presenting to Investigators with transtibial amputations and who are currently using a passive prosthetic device will undergo evaluation for potential participation in the study.

A subject will sign the study-specific informed consent form (ICF) prior to performing any test involved in determining eligibility that goes beyond standard of care.

Each subject must meet the inclusion/exclusion criteria for this study to be eligible for study participation.

9.2. *Moment of Enrollment*

Subjects will be considered “enrolled” in the study once compliance with all inclusion and exclusion criteria has been verified and documented; and the subject has signed the informed consent form. At that point, the subject will enter the baseline phase of the study.

9.3. *Subject Identification*

Each subject will be assigned a unique subject identification number at the time of consent. This subject identification number will be retained throughout the study if the subject is enrolled. Sites will keep a log that notes the subject’s name and corresponding subject identification number. All case report forms (CRFs) will be tracked, evaluated, and stored using only the subject ID number and initials. No personal other identifying information will be included on the CRFs.

The ICF will notify subjects that study monitors, auditors, and representatives of government agencies will have access to personal identifying information to ensure that data reported on the CRFs corresponds to the person who signed the ICF and the information contained in the source documentation.

9.4. *Phase I: 1st Visit - Baseline*

For each of the enrolled subjects, characteristics at the time of the procedure including: age, sex, weight, amputation side(s) and amputation type(s), medical history will be recorded. At day of enrollment, subjects will complete:

- Amputee Mobility Predictor (AMP)
- Physical Assessment
- Fitted with a Fitbit® One™ activity tracker
 - The activity tracker will to be used to monitor steps taken on their passive prosthetic device for 14 days. A minimum of twenty-seven hundred (2700) recorded daily steps while using the passive prosthesis will be documented toward ability to perform the study’s 6MWT. [12]
- Subjects will be provided a patient diary to track activity, falls and self-reporting of activities of daily living.

9.5. *Phase I: 2nd Visit - Study Procedure*

At the second visit, the subject will complete the following study assessments wearing the passive prosthetic:

- 6MWT
- Ramp Ascent
- Ramp Descent
- ABC Scale
- Falls Efficacy Scale
- Mobility PLUS-M (12 item Short Form)
- PROMIS Questionnaires

At the end of the second visit, subjects will be fitted with the emPOWER Ankle by a qualified clinical prosthetist, trained by BionX personnel. This fitting includes selection of the appropriate size and category carbon fiber foot, alignment, and tuning in accordance with the emPOWER Instructions For Use (IFU). The prosthetist will make a determination that the tuning was successful (within the bounds specified by the IFU) and the Investigator will maintain a copy of the Tuning Record. This initial Tuning Record may also be used to verify that the subject has the ability to walk at a self-selected walking speed (SSWS) > 0.75 meters per second with the current prosthesis and can walk with variable cadence, where variable cadence is defined as three distinguishable walking speeds with a minimum SSWS of 0.75 m/s (one below SSWS, and one above SSWS) on the Tuning record. Distinguishable will be defined as no overlap between the three (3) primary step groupings for each walking speed displayed on the Tuning Record.

At fitting of the emPOWER Ankle, the Investigator will instruct the subject to utilize the device for a 16-day period of time, within the intended and foreseeable range of use (e.g. – ramps, stairs, limited running or jumping, stepping sideways, etc.). In addition, the investigator will take the subject through a series of default operating conditions of the emPOWER Ankle in the clinic setting such as with the power turned off.

Each subject will take the emPOWER Ankle (including batteries and charger) home for 16 days (to ensure 14 full days of step counts) of use in everyday life situations. The subject will not be under the observation of the Investigator during this take home period. During the at home portion of the study, subjects will continue to monitor daily steps with use of a Fitbit® One™ during the time that they are wearing the emPOWER Ankle. Subjects will also maintain an Activities of Daily Living Diary during the take home evaluation portion of the study. This Diary will allow subjects to note specific activity changes due to the emPOWER Ankle and serve as a log for recording any falls.

As a quality check, the steps on the emPOWER Ankle, as recorded in the emPOWER Tuning Records, will also be recorded at baseline and at follow-up.

9.6. *Phase I: 3rd Visit - emPOWER Follow Up*

After the 16-day period of use, the subject will return to the prosthetist. The window for this visit is +1 week.

During this visit, the subject will complete the following study assessments wearing the emPOWER Ankle:

- 6MWT
- Ramp Ascent
- Ramp Descent
- AMP
- ABC Scale
- Falls Efficacy Scale
- Mobility PLUS-M (12 item Short Form)
- PROMIS Questionnaires

In addition, the patient diary will be reviewed for Fitbit steps, falls and daily activity.

The Investigator will maintain a copy of the Tuning Record.

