7.1. Selection Criteria

Study inclusion and exclusion criteria for the study are included in Table 7.1.1 below. Prior to enrollment in the study, a subject must meet all of the inclusion criteria and none of the exclusion criteria.

Table 7.1.1: Selection Criteria

| |
|--------------------|
| Selection Criteria |
|--------------------|

| Selection Criteria | |
|---------------------------|---|
| Inclusion Criteria | 
 I-1. Male and Female I-2. 55 years or older I-3. Subjects with transtibial amputations of either leg at least 1-year prior I-4. Suction or elevated vacuum suspension and Socket Comfort Score of at least 6 I-5. Sock fluctuation of ≤ 8 ply per day I-6. K-level rating of 3 or 4 based on the AMP score I-7. Ability to walk at a walking speed of > 0.75 meters per second with the current prosthesis I-8. Unilateral amputees (up to 7 bilateral amputees can be included, 1 per site in addition to the unilateral amputees) I-9. Foot size: 25-30 cm I-10. Ability to complete a continuous 6MWT I-11. Ability to provide written, informed consent I-12. Ability to complete study visits and study documents I-13. Ability to manage the complexity of a powered device including charging and changing batteries as needed I-14. Ability to read and understand English |
| Exclusion Criteria | 
 E-1. Subjects who have never used a prosthetic device E-2. Less than 55 years of age E-3. Weight <150 lbs. or > 287 lbs E-4. Transfemoral amputees E-5. Active sores or ulceration on subject's residual limb E-6. Sore on contralateral foot E-7. Cuff-link socket suspension E-8. Socket Comfort Score of less than 6 E-9. Sock fluctuation of > 8 per day E-10. K level of 1 or 2 E-11. Amputation clearance < 8.625" E-12. History of stroke or TIA that impairs current walking E-13. Recent history of excessive falling defined as more than 2 falls requiring medical assistance in the prior year |

| Selection Criteria | |
|--------------------|---|
| | E-14. Medications potentially affecting balance |
| | E-15. Recent hospitalization (within past 3 months) |
| | E-16. Cognitive deficiency that would impact ability to charge and change batteries as needed |

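### Could the emPOWER Tuning Record, made after enrolment, end up deciding the walking-speed criterion I-7?

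*Combined protocol and SAP*

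**What the plan says.** Criterion I-7 in Table 7.1.1 reads: "Ability to walk at a walking speed of > 0.75 meters per second with the current prosthesis". It names no pace. Section 7.1 fixes the timing: "Prior to enrollment in the study, a subject must meet all of the inclusion criteria and none of the exclusion criteria". Section 9.2 counts a subject as enrolled only "once compliance with all inclusion and exclusion criteria has been verified and documented" and consent is signed. Section 9.1 describes candidates as people "who are currently using a passive prosthetic device", and it allows, after consent, for "any test involved in determining eligibility that goes beyond standard of care". Table 9.11.1 places the Eligibility Assessment at Visit 1 only.

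Section 9.5 covers Visit 2. It begins with passive testing, including the 6MWT: "At the second visit, the subject will complete the following study assessments wearing the passive prosthetic". The emPOWER is fitted and tuned at the end of that visit. The section then adds: "This initial Tuning Record may also be used to verify that the subject has the ability to walk at a self-selected walking speed (SSWS" greater than 0.75 m/s on the current prosthesis, and that the subject "can walk with variable cadence, where variable cadence is defined as three distinguishable walking speeds with a minimum SSWS of 0.75 m/s". The double-asterisk footnote of Table 9.11.1 says the Visit 2 Tuning Record confirms the walking speeds needed for the emPOWER arm.

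**The concern.** Section 9.5 repeats I-7's threshold and its reference to the current prosthesis, yet the evidence it offers comes from the emPOWER fitting. That is after enrolment, so it cannot show that a pre-enrolment condition was met. It is probably also on the wrong device. Section 2.1 says tuning values come from sensors inside the prosthesis, and the end of Section 9.5 says the records hold steps taken on the emPOWER.

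The three places also differ in content. Section 9.5 brings in self-selected pace and variable cadence, which Table 7.1.1 lacks. It uses both a strict and a non-strict 0.75 m/s. The footnote treats the speeds as required without saying what follows if they are not reached.

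If speed on the emPOWER decided entry, people who do well on it would be favoured. Suppose a subject walks at 0.65 m/s on the passive device and 0.75 m/s on the emPOWER. That subject fails I-7, and the 6MWT distances are 0.65 × 360 = 234 m and 0.75 × 360 = 270 m. The Section 11 outcome would be 100 × 36 / 234 = +15.4%, from one subject in a study of at most ten.

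**Working it through.** **Order of events.**

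| Step | Where stated | Device |
|---|---|---|
| I-7 met, verified and documented; subject enrolled | 7.1, 9.2; Visit 1 in Table 9.11.1 | passive |
| 14 days of step monitoring | 9.4 | passive |
| Visit 2 tests, including 6MWT | 9.5 | passive |
| Fitting and initial Tuning Record | 9.5, end of Visit 2 | emPOWER (inferred) |
| Primary 6MWT on emPOWER | 6.1, 9.7 | emPOWER |

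The record comes after the eligibility decision, so a site that follows 7.1 and 9.2 cannot use it to make that decision.

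**What the record can do afterwards.** Section 9.5 uses permissive wording and presents this as an additional use. No section withdraws a subject because of the record. Section 7.2 replaces only subjects withdrawn before they walk on the emPOWER, and Section 16.1 keeps all subjects' data in the report. The record therefore has no route into the analysis set.

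**Size.** The plan gives no figure to reproduce, and the analysis is descriptive. The following is illustrative and every input is assumed:

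- Passive speed is normal with mean μ and SD 0.15 m/s.
- The device difference has mean g and SD D (0.05 to 0.10).
- Test error has SD e (0.03 to 0.07) and is independent between tests.
- ρ is the correlation between the fitting-day and the 3-month device difference.
- Self-selected speed equals 6MWT speed.

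*Route 1, the plan as written.* I-7 is verified on the passive device before enrolment. Its error is independent of the later tests, so the bias in the mean difference is 0 m.

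*Route 2, a departure in which the record alone decides.* With s = √(0.15² + D² + e²), a = (μ + g − 0.75)/s and λ = φ(a)/Φ(a), the bias is 360 × ρ × (D²/s) × λ.

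- μ = 0.9, g = 0, D = 0.10, e = 0.07: s = √0.0374 = 0.1934, a = 0.776, λ = 0.378. Bias = 360 × (0.01/0.1934) × 0.378 × ρ = 7.04ρ m.
- Same with g = 0.10, the gain that Section 10.2 equates to 36 m: a = 0.25/0.1934 = 1.293, λ = 0.192. Bias = 3.57ρ m.
- Across the assumed D and e at μ = 0.9 and ρ = 1: 1.8 to 7.1 m with g = 0, and 0.7 to 3.6 m with g = 0.10.
- Slowest case, μ = 0.8, g = 0, D = 0.10, e = 0.03: 12.45ρ m.

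*Route 3, I-7 verified properly but subjects then dropped on the record.* With g = 0, D = 0.10 and e = 0.07: 5.36ρ m at μ = 0.9 and 8.32ρ m at μ = 0.8.

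*Sampling error for scale.* SE = 360 × √(D² + 2e²)/√n.

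- D = 0.10, e = 0.07: 360 × √0.0198/√10 = 16.0 m, and 22.7 m at n = 5.
- D = 0.10, e = 0.03: 360 × √0.0118/√10 = 12.4 m.

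*Subjects admitted who truly fail I-7, μ = 0.9.*

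- g = 0, D = 0.10, e = 0.03: 5.32% if the record decides, against 2.02% with a passive walk, an excess of 3.3 points.
- g = 0.10, D = 0.05, e = 0.03: 10.7% against 2.0%, an excess of 8.7 points.

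The excess depends on the assumed gain, so no general bound can be given.

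**The case for a change.** The strongest case for acting is that the Tuning Record is the only source the protocol names for I-7. No timed walk is scheduled at Visit 1: the 6MWT and ramp tests start at Visit 2, and the 10MWT and L-Test at Visit 4. The footnote speaks of required speeds, so a site could treat the record as a gate. Any resulting bias would be zero or would favour the emPOWER, in an open-label study whose stated purpose includes reimbursement. The cost would be a few words and one short walk.

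The mismatch in wording stands, and so does the remark that the Visit 1 check is not itemised. Neither carries the point further. Protocols seldom say how each criterion is checked: socket comfort in I-4 and sock fluctuation in I-5 have no scheduled procedure either. Section 9.1 foresees eligibility tests, and a prosthetic clinic can readily time a walk. A different reading of Section 9.5 is also open, in which it describes a set-up check on the newly fitted device. That reading fits the footnote and the added cadence condition, although the wording shared with I-7 weighs against it.

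Writing in a timed walk would not change the expected result on the compliant route, which is already unbiased. It would still admit 2.0% to 4.0% true failures at a mean of 0.9 m/s, and a self-selected walk would add a pace that I-7 does not specify. The strict versus non-strict threshold matters only at exactly 0.75 m/s.

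**Conclusion.** No change to the plan follows. The text is untidy across Section 9.5, Table 7.1.1 and the footnote, but Sections 7.1 and 9.2 govern and settle I-7 before the record exists. On that route the bias is 0 m, and this conclusion rests only on the order of events and on no section excluding anyone because of the record.

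The non-zero figures need a site to depart from the protocol and rest wholly on assumed spreads, mean speed, device effect and ρ. At a mean of 0.9 m/s they stay below the matching standard error. In the slowest case considered, with full persistence of the device difference, the bias reaches about one standard error at ten subjects (12.45 m against 12.4 m). They do not estimate what this study will show.

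That the record reflects walking on the emPOWER is a strong inference, not a stated fact. Even if it is correct, a descriptive pilot reporting all its subjects loses nothing by it. Anyone wanting reassurance can read the Visit 2 passive 6MWT, taken before the fitting, against 270 m (0.75 × 360). That uses data already collected and should serve as description only, because 6MWT pace need not equal self-selected pace.

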9.7. Phase II: 4th Visit – 3 Month Visit

Subjects will be invited to participate in long-term follow-up. For a minimum of 14 days prior to this visit, the subject should wear the Fitbit and complete the patient diary for steps, fall and daily activity.

Subjects will be seen by the prosthetist after wearing the emPOWER Ankle for 3 months. The window for this visit is -1 week / + 6 weeks.

During this visit, the subject will complete the following study assessments wearing the emPOWER Ankle:

- 12MWT (with distance walked assessed at 6 and 12 minutes)
- 10MWT
- L-Test
- Ramp Ascent
- Ramp Descent
- ABC Scale
- Falls Efficacy Scale
- AMP
- Mobility PLUS-M (12 item Short Form)
- PROMIS Questionnaires
- Patient-specific Functional Scale (PSFS)
- Numeric Pain Rating Scale (NPRS)

In addition, the patient diary will be reviewed for Fitbit steps, falls and daily activity.

At the end of the study visit, subjects will return to wearing their passive prosthetic foot for 2-4 weeks of re-accommodation.

The subjects are reminded to wear the Fitbit activity monitor and complete the patient diaries to track activity, falls and self-reporting of activities of daily living.

9.8. Phase II: 5th Visit – Crossover Visit

Subjects will be seen by the prosthetist after wearing their passive prosthetic foot for 2-4 weeks. The window for this visit is 2-6 weeks after passive device fitting.

For a minimum of 14 days prior to this visit, the subject should wear the Fitbit and complete the patient diary for steps, falls and daily activity.

During this visit, the subject will complete the following study assessments wearing the passive prosthetic:

- 12MWT (with distance walked assessed at 6 and 12 minutes)
- 10MWT
- L-Test
- Ramp Ascent
- Ramp Descent
- ABC Scale
- Falls Efficacy Scale
- AMP
- Mobility PLUS-M (12 item Short Form)
- PROMIS Questionnaires
- PSFS
- NPRS

At the end of the study visit, subjects will return to wearing the emPOWER Ankle for the remainder of the study. If there are any adjustments to the tuning settings different from those previously used for the emPOWER Ankle, the tuning record should be saved.

9.9. ***Phase II: 6th Visit – 6 Month Visit***

Subjects will be seen by the prosthetist. The window for this visit is -4 weeks / + 3 months.

During this visit, the subject will complete the following study assessments wearing the emPOWER Ankle:

- 12MWT (with distance walked assessed at 6 and 12 minutes)
- 10MWT
- L-Test
- Ramp Ascent
- Ramp Descent
- ABC Scale
- Falls Efficacy Scale
- AMP
- Mobility PLUS-M (12 item Short Form)
- PROMIS Questionnaires
- PSFS
- NPRS

If there are any adjustments to the tuning settings for the emPOWER Ankle, the tuning record should be saved.

9.10. ***Phase II: 7th Visit – 12 Month Visit (Final Study Visit)***

Subjects will be seen by the prosthetist. The window for this visit is -3 months / + 3 months. This will be the final study visit.

During this visit, the subject will complete the following study assessments wearing the emPOWER Ankle:

- 12MWT (with distance walked assessed at 6 and 12 minutes)
- 10MWT
- L-Test
- Ramp Ascent
- Ramp Descent
- ABC Scale
- Falls Efficacy Scale
- AMP
- Mobility PLUS-M (12 item Short Form)
- PROMIS Questionnaires
- PSFS
- NPRS

9.11. **Table 9.11.1: Procedures and Assessments**

The following table summarizes the timing and specific assessments to be conducted in this study:

| ASSESSMENT | BASELINE 1ST Visit | PASSIVE DEVICE ASSESSMENT/ ANKLE FITTING 2nd Visit | emPOWER Follow-Up 3rd Visit | 3 MONTHS 4th Visit | CROSSOVER 5th Visit | 6 MONTHS 6th Visit | 12 MONTHS 7^h Visit |
|---|---|--|--|--|---|--|--|
| Visit Window | | | 16 days after Visit 2 +1 week | -1 week / + 6 weeks | 2-6 weeks after passive device fitting | -4 weeks / + 3 months | -3 months / + 3 months |
| Eligibility Assessment | X | | | | | | |
| ICF ^a | X | | | | | | |
| Demographics (DOB, Gender) | X | | | | | | |
| Physical Assessment (ht, wt, side and type of amputation) | X | | | | | | |
| Medical History | X | | | | | | |
| AMP | X | | X | X | X | X | X |
| FitBit One™ steps | + | X | X | X | X | | |
| Tuning Record | | X** | X | | *** | *** | *** |
| 6MWT | | X | X | | | | |
| 12MWT (includes 6 min distance, pain-free walking scale and BORG RPE) | | | | X | X | X | X |
| 10 MWT | | | | X | X | X | X |
| L-Test | | | | X | X | X | X |
| Ramp Test (Ascent & Descent) | | X | X | X | X | X | X |
| ABC | | X | X | X | X | X | X |
| Falls Efficacy Scale | | X | X | X | X | X | X |
| PLUS-M | | X | X | X | X | X | X |
| PROMIS Evals | | X | X | X | X | X | X |
| PSFS | | | | X | X | X | X |
| NPRS | | | | X | X | X | X |
| EASE Study Activity Diary (Reviewed) | + | X | X | X | X | | |
| Adverse Events & Concomitant Medication | X | X | X | | X | X | X |

+ FitBit One™ and diary provided to Subject

^a If the study ICF is modified during the course of the study, study subjects will be re-consented.

** Confirms walking speeds required for emPOWER Ankle arm

*** Collect the tuning record if adjustments are made to the emPOWER device

10. Study Assessments

10.1. *Amputee Mobility Predictor (AMP)*

The AMP is an instrument designed to measure ambulatory potential of lower-limb amputees [13]. Subjects begin the test seated in a hard chair with arms and are tested for a total of 21 items assessing abilities of increasing level of difficulty. Abilities assessed include sitting balance, transfer from chair to chair, standing balance, gait quality, negotiating obstacles, and the use of assistive devices. The total score range for the AMP is 0 to 47 points. A minimal detectable change of 3.4 points has been reported [14].

10.2. *12-Minute Walk Test (and 6-Minute Walk Test) (12MWT & 6MWT)*

The walking test is a validated performance test used to measure gait speed and aerobic capacity/endurance. The distance that the patient is able to walk in 6 and 12 minutes is recorded. In addition, subjects will be asked to indicate when they experience an onset of pain, if occurring during the test, to determine the pain-free walking distance. Assistive device may be used, but should be recorded and consistent between tests. Minimally clinically important differences (MCID) have not yet been reported for amputees, but for patients with incomplete spinal cord injury (36 m) [15] and stroke (34.4 m) [16]. Generally in rehabilitation, increases in walking speed of 0.1 m/s or more, which would equal an increase in walking distance of 36 m or more in the 6MWT, are considered clinically meaningful [17-19]. The distance a subject can walk after 6 and 12 minutes while wearing the emPOWER Ankle compared to the subject's passive prosthesis.

The Borg Rating of Perceived Exertion (RPE) score will also be recorded at 6 and 12 minutes and assessment of pain-free walking distance for sound and residual knee and hip, low back pain for subjects that report such pain during the 12minWT. The RPE measures the perceived intensity of physical activities on a visual analogue scale and provides a good estimate of the actual heart rate during physical activity and is correlated with lactate levels, %VO₂max, and breathing rates in athletes [20].

10.3. *10-Meter Walk Test (10MWT)*

The walking test is a validated test used to measure gait speed. When available, data will be collected for the walking tests. Subjects are often allowed the use of walking aids (such as a cane, crutches or hemi-walker) that they normally use in home or community ambulation. In addition to the time to complete the test, the use of walking aids, the distance of the walk test and the use of footwear (e.g. barefoot or with shoes) will be recorded.

10.4. *L-Test*

The L-Test is a timed 20-meter test of basic mobility skills that includes 2 transfers and 4 turns at the subject's usual walking speed. This test is a modified version of the Timed Up and Go Test designed for people with lower limb amputations. The test is measured by the time that it takes a subject to stand from an armless chair, walk 10 meters (in the shape of an L) at the subject's usual walking speed, turn 180 degrees, and return 10 meters (in the shape of an L) back to a seated position in the same chair [21]. The L-test was selected, since it measures overall functional mobility risk and fall and is validated for the amputee population. The time to

perform the L-Test with the emPOWER Ankle will be compared to the time on subject's passive prosthesis.

10.5. ***Ramp Tests (Ascent and Descent)***

The ramp ascent test is a timed performance test of walking up a 25-foot ramp with 5 degree incline and an outdoor hill (length and inclination/grade to be determined). The ramp ascent time with the emPOWER Ankle will be compared to the time on the subject's passive prosthesis followed by the Hill Assessment Index. The Hill Assessment Index is an instrument to measure the quality of the subject's gait during ramp ambulation.

The ramp decent test is a timed performance test of walking down a 25-foot ramp with 5 degree incline and an outdoor hill (length and inclination/grade to be determined). The ramp decent time with the emPOWER Ankle will be compared to the time on the subject's passive prosthesis followed by the Hill Assessment Index and questionnaire assessing patient-perceived control of walking speed.

10.6. ***Activities-Specific Balance Confidence (ABC) Scale***

The ABC Scale [22] is a self-administered questionnaire that asks the patient to rate his or her confidence in performing various ambulatory activities on a scale from 0% (no confidence) to 100% (complete confidence) without losing balance or becoming unsteady. Scores for each of the 16 items will be collected and an average percentage calculated, with scores <67 indicating an increased risk of falling [23]. The scores on the ABC with the emPOWER Ankle will be compared to the subject's passive prosthesis.

10.7. ***Falls Efficacy Scale***

The Falls Efficacy Scale is a validated 10-item self-report questionnaire designed to assess confidence in the ability to perform 10 activities of daily living without falling as an indicator of how one's fear of falling impacts physical performance. Each item is rated from 1 ("very confident") to 10 ("not confident at all"), and the per item ratings are added to generate a summary total score (10 to 100). Lower scores indicate more confidence and higher scores indicate lack of confidence and greater fear of falling. It has been validated for use in the elderly [24] and persons with amputations [25]. Scores ≥ 70 indicate an increased fear of falling. [24, 25]

10.8. ***Prosthetic Limb Users Survey-M (PLUS-M)***

The PLUS-M is a valid and reliable self-reported measure for the mobility of adults with lower limb amputations. PLUS-M asks about the patient's ability to perform simple and complex tasks. This questionnaire is asking about the current timeframe for the patient. High PLUS-M scores correspond with greater mobility [26]. The scores on the PLUS-M with the emPOWER Ankle will be compared to the scores on the subject's passive prosthesis.

10.9. ***PROMIS Instruments***

PROMIS item banks and their short forms are a reliable and precise measurements of patient reported outcome measures [27]. For this study, the following instruments will be used: the PROMIS Physical Function (Custom), the PROMIS Global Health Short Form, the PROMIS Fatigue Short Form (7a), and The PROMIS Pain Intensity Short Form (3a). The scores on the

PROMIS instruments with the emPOWER Ankle will be compared to the scores on the subject's passive prosthesis.

10.10. *Patient Specific Functional Scale (PSFS)*

The PSFS [28] is a self-report measure aimed at identifying functional status limitations that are most relevant to individual patients. The PSFS is a reliable, valid, and efficient measure for detecting clinical change in persons with low back pain and knee dysfunction [29]. Patients will be asked to identify three to five activities that they are having difficulty or are unable to perform because of their injury/condition. For the specified activities, patients will then be asked to rate their ability to perform each activity at that time (0-10 numerical scale) with '0' being unable to perform the activity, and '10' being able to perform the activity at the same level as they could prior to the injury/condition. The scores on the PSFS instruments with the emPOWER Ankle will be compared to the scores on the subject's passive prosthesis.

10.11. *Numeric Pain Rating Scale (NPRS)*

The NPRS is a valid and reliable measure of pain that may be used across all musculoskeletal injuries/conditions and complements the PSFS [29]. The patient will be asked to rate the pain of their joints, foot, lower back, and if they are using an assistive device any additional affected limbs on average over the last 24 hours on a scale 1-10, with '1' being 'very mild' and '10' being the 'unimaginable unspeakable'. The scores on the NPRS instruments with the emPOWER Ankle will be compared to the scores on the subject's passive prosthesis.

10.12. *Activity Monitoring*

An activity monitor will be worn to record the number of steps the patient takes with the prosthesis. The patient will return to the site with the activity monitor so that the steps counted can be downloaded from the device. In addition, the patient will be sent home with a prepaid envelope and be instructed to mail back the activity monitor if the next visit will be more than 3 weeks later, to ensure that the data is not lost. The step counts will be downloaded from the device the day the activity monitor is returned to the Investigator. The Investigator will record the date the patient was affixed with the activity monitor, the date they received the returned activity monitor, and the date they synced the monitor.

10.13. *Subject Diary (Activity Monitoring)*

Subjects will be provided with a 'diary' to record a daily step-count (using the Fitbit provided), falls and daily activity. Subjects will record positive and negative observations about the prosthesis performance while wearing the study devices. These observations will be reviewed together with the Investigator during the study visits. In addition, subjects will also record in the diary any falls and resulting injuries. If any of the diary entries reveal complaints or adverse events, these will be reported on the Adverse Event form.

11. Statistical Methods

The study objective is to characterize the improvement in the 6MWT with the emPOWER Ankle versus the subject's passive lower-limb prosthesis. This is calculated as:

Percent change in 6MWT=100 * (emPOWER Ankle 6MWT – Passive Prosthesis 6MWT) / Passive Prosthesis 6MWT

A positive value for Percent Change in 6MWT represents the percent increase in the 6MWT, and a negative value represents a decrease.

12. Adverse Events

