6.2. Secondary Endpoints

The secondary endpoints of this study will compare the following assessments on the emPOWER Ankle to the subject’s passive prosthesis at Baseline (before wearing the emPOWER, when available) and Crossover:

- 12 minute Walk Test (12MWT)
- 10 meter Walk Test (10MWT)
- L-Test for overall mobility and fall risk
- Time and Quality of Ramp Ascent
- Time and Quality of Ramp Descent
- Activities-specific Balance Confidence (ABC) Scale
- Falls Efficacy Scale
- Amputee Mobility Predictor (AMP) Assessment
- Prosthetic Limb Users Survey of Mobility (PLUS-M) (12 item Short Form)
- Patient-specific Functional Scale (PSFS)
- Numeric Pain Rating Scale (NPRS)
- Activity monitoring
- Falls
- Activity Diary
- PROMIS Physical Function (Custom)
- PROMIS Global Health Short Form
- PROMIS Fatigue Short Form (7a)
- PROMIS Pain Intensity Short Form (3a)

Long term follow-up of subjects who agree to continue wearing the emPOWER Ankle at 3, 6 and 12 months with all outcome measures (except the diaries of activity and falls at 6 & 12 months).

7. Study Population

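### As Section 10.11 defines it, the NPRS has no value for a pain-free site, so a change to or from no pain is understated by one point or lost as a blank

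*Combined protocol and SAP*

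**What the plan says.** Section 6.2 names the "Numeric Pain Rating Scale (NPRS") among the secondary endpoints. Section 10.11 defines it: "The patient will be asked to rate the pain of their joints, foot, lower back", and other affected limbs if an assistive device is used, averaged over the last 24 hours, "on a scale 1-10, with '1' being 'very mild" at the lower end and "10' being the 'unimaginable unspeakable" at the upper end. The stated use is a comparison of devices: "The scores on the NPRS instruments with the emPOWER Ankle will be compared to the scores on the subject's passive prosthesis".

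No section gives a zero, a no-pain option, a not-applicable code or an instruction for a site without pain. By contrast, the PSFS in Section 10.10 has a true lower end point ("0-10 numerical scale) with '0' being unable to perform the activity").

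Table 9.11.1 and Sections 9.7 to 9.10 place the NPRS at Visits 4 to 7. Of these, only the Crossover visit (Visit 5) is done on the passive prosthesis.

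**The concern.** The lowest permitted score is already a pain state, yet subjects are asked about a fixed set of sites whether or not those sites hurt. A subject with no pain in, say, the lower back has no correct answer under the stated rule and must either enter 1 or leave the item empty. The protocol does not say which, so practice could differ between subjects, or between visits in one subject.

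Pain-free sites are to be expected. No entry criterion requires pain, and Section 10.2 treats pain on the walk test as conditional ("if occurring during the test, to determine the pain-free walking distance"). How common they are is not stated.

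At stake is the device comparison on this endpoint. The changes affected are those in which pain at a site disappears or newly appears. The passive side of the comparison rests on one visit, and a no-pain answer that was never offered cannot be recovered later.

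**Working it through.** The plan states no NPRS effect size, standard deviation or sample-size figure, so there is nothing to reproduce. The check is a reading of the scale followed by arithmetic.

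**Inputs from the documents.** Scale of 1 to 10 with 1 meaning very mild; several sites; within-subject comparison of devices (all Section 10.11). Descriptive analysis and up to 10 subjects (Protocol Synopsis).

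**Inputs assumed, because the documents give neither.** The share q of site ratings that are pain-free, taken as 0.2, 0.5 or 0.8. The mean score m at painful sites, taken as 3 and varied from 1 to 4. A simple mean over site ratings is also assumed, since no NPRS summary score is defined.

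**Step 1: one site, no pain entered as 1.** A change from score a to no pain is truly -a, but is recorded as 1 - a:

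- very mild (1) to none: true -1, recorded 0
- 2 to none: true -2, recorded -1
- 3 to none: true -3, recorded -2
- 4 to none: true -4, recorded -3

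The loss is always one point. It is the same in reverse: new very mild pain at a previously pain-free site is truly +1 and is recorded as 0. A site that is pain-free on both devices reads 1 - 1 = 0, which is correct. A site painful on both devices is unaffected. This step needs no assumption about q or m.

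**Step 2: mean level on one device.** True mean = (1 - q) x m. With no pain entered as 1, recorded mean = (1 - q) x m + q. With no pain left blank, recorded mean = m. For m = 3:

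| q | True mean | No pain entered as 1 | No pain left blank |
|---|---|---|---|
| 0.2 | 2.4 | 2.6 | 3.0 |
| 0.5 | 1.5 | 2.0 | 3.0 |
| 0.8 | 0.6 | 1.4 | 3.0 |

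**Step 3: difference between devices, no pain entered as 1.** Recorded change = true change + (q on emPOWER - q on passive). If the two shares are equal, the offset cancels. If the share rises from 0.2 on passive to 0.5 on emPOWER with m = 3, the true change is 1.5 - 2.4 = -0.9 and the recorded change is 2.0 - 2.6 = -0.6, a loss of 0.3 / 0.9 = one third. With the same shares, m = 1 gives -0.3 recorded as 0, and m = 4 gives -1.2 recorded as -0.9.

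**Step 4: difference between devices, no pain left blank.** If m is the same on both devices, the recorded means are both m and the recorded change is 0 whatever the shares. A site that became pain-free has no second value, so it cannot be told apart from a skipped item.

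**The case against.** The strongest objection is that the NPRS form itself is not in the documents. Section 10.11 may be a loose summary of a form that does offer a none box, in which case no data would be misrecorded. That limits what can be said about the data, but it does not rescue the text: Section 10.11 would then contradict the form and would still need correction.

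A reader might also infer that NPRS scores are inflated by a known amount, or that the scale hides any benefit on mild pain. The documents support neither. The shares in the working are assumptions. The planned use is a within-subject comparison, in which sites pain-free on both devices cancel when scored 1, and no NPRS level or cut-off is to be interpreted. With no pain scored as 1, only the step between very mild and none disappears; larger changes to no pain still show, one point short.

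Nor do the documents show that pain-free sites are common. K-level and Socket Comfort Score do not measure joint, foot or back pain, and the subjects are amputees aged 55 or older. Pain-free sites are plausible, but their frequency is unknown.

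Finally, the NPRS is one of 18 listed secondary endpoints, and pain is measured in other ways. "The PROMIS Pain Intensity Short Form (3a") is collected at Visits 2 to 7, with passive-device assessments at both Visit 2 and Crossover, and pain-free walking distance is recorded with the walk test. This cover is real but partial: the documents do not describe the PROMIS form as rating the separate sites that the NPRS covers.

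**Conclusion.** The point stands in a limited form. As written, Section 10.11 gives no value for a pain-free site. If such sites are entered as 1, each within-subject change to or from no pain is understated by exactly one point, in either direction. If they are left blank, the mean describes painful sites only and a change to no pain looks like missing data.

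The one-point loss per site follows from the scale alone. The effect on a device mean depends on the pain-free shares, which the documents do not give; the 0.3-point loss in the example is an illustration under stated assumptions, not an estimate.

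The consequence is confined to one secondary endpoint in a single-site descriptive pilot of up to 10 subjects. The primary 6MWT endpoint is untouched. The change is worth making because the defect is plain in the text and cheap to remove.

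**What to change.** In Section 10.11 and on the CRF, define the NPRS as 0-10 with 0 meaning no pain, for every rated site and at every NPRS visit (Visits 4 to 7). State that each site is to be answered, so that a blank means only missing. If the form in use already has a no-pain option, correct Section 10.11 to match it instead.

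The cost is one line in the protocol and, if needed, a CRF edit. No visit or test is added.
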